	
The point estimates for the primary and secondary endpoints will be calculated along with 95% confidence interval and by companion diagnostic (CDx) status (CDx+ or CDx-).
 
Adverse Events:
 
AEs will be coded using the most current version of Medical Dictionary for Regulatory Activities (MedDRA®).
 
A by-subject AE data listing, including verbatim term, preferred term (PT), system organ class (SOC), treatment, severity, seriousness criteria, relationship to drug, and action taken, will be provided.
 
The number of subjects experiencing treatment-emergent adverse events (TEAEs) and number of TEAEs will be summarized by treatment using frequency counts in safety analysis set.
 
Medical History, chest x-ray, electrocardiogram (ECG), and physical examination will be listed by subject.
 
Changes in ECGs and physical examinations will be described in the text of the final report.
 
Concomitant Medications:
 
Concomitant medications will be coded using the most current World Health Organization (WHO) drug dictionary and listed by treatment.
 
Pharmacokinetics:
 
Summary statistics of PRA023 concentrations and ADA by visit.

--	--

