#### 3.1 Primary Endpoints

- Safety and tolerability: the proportion of subjects reporting AEs, SAEs, AEs leading to discontinuation, and markedly abnormal laboratory values
- The proportion of subjects with endoscopic improvement, as defined by decrease in SES-CD  $\geq 50\%$  from Baseline at Week 12

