### **9.2.7 Evaluation of Safety Parameters**

#### **9.2.7.1 Adverse Events and Adverse Events of Special Interest**

All AEs will be coded using most current version of Medical Dictionary for Regulatory Activities (MedDRA). All reported adverse events will be assigned to the SOC and PT according to MedDRA. The number and percentage of subjects reporting AEs (all, serious, related) will be

tabulated by overall and treatment. AEs will be summarized by SOC and PT. AEs will also be summarized by relationship to the study drug, seriousness, and severity.

A treatment-emergent AE (TEAE) will be defined as an AE that began or worsened on or after the first treatment dose. AEs recorded prior to the first infusion of study treatment will be considered non-treatment-emergent.

All reported AEs (treatment-emergent or not) will be listed. Only TEAEs will be summarized.

AEs of special interest including infections, acute infusion reaction (within 1 hour of completion of infusion), and peri-infusion reaction (within 24 hours of completion of infusion) will be summarized based on a pre-specified MedDRA list.

AEs occurring in subjects who are considered immunogenicity positive will also be summarized.

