2 STUDY OBJECTIVES AND ENDPOINTS

This is a Phase 2a, Multi-Center, Open-Label Study to Evaluate the Safety, Efficacy, and Pharmacokinetics of PRA023 in Subjects with Moderately to Severely Active Crohn’s Disease. The primary, secondary and exploratory study objectives and corresponding endpoints for IP analyses are listed in **Table 1** below.

Table 1 Study Objectives and Endpoints

Objectives	Endpoints
Primary	
To evaluate the safety and tolerability of PRA023 following 12-weeks of induction therapy	
 Proportion of subjects reporting AEs, SAEs, AEs leading to discontinuation, and markedly abnormal laboratory values
To assess the proportion of subjects with endoscopic improvement (decrease in simple endoscopy score for Crohn’s disease [SES-CD] \geq 50% from Baseline) at Week 12	
 Proportion of subjects with endoscopic improvement , as defined by decrease in SES-CD \geq 50% from Baseline at Week 12
Secondary	
To assess the proportion of subjects with clinical remission (Crohn’s disease activity index [CDAI] < 150) at Week 12	
 Proportion of subjects in clinical remission (CDAI < 150) at Week 12
To assess the proportion of subjects with endoscopy and clinical improvement at Week 12	
 Proportion of subjects with endoscopic and clinical improvement, as defined by decrease in SES-CD \geq 50% AND reduction in CDAI \geq 100 points from Baseline or CDAI <150 at Week 12
To assess the proportion of subjects with biomarker and clinical improvement, among subjects with at least one elevated biomarker at Baseline, at Week 12	
 Proportion of subjects with both biomarker and clinical improvement (decrease in hsCRP OR fecal calprotectin \geq 50% from Baseline, among subjects with at least one elevated biomarker at Baseline, AND reduction in CDAI \geq 100 points from Baseline or CDAI <150) at Week 12

To assess the proportion of subjects with normalization of C-reactive protein (hsCRP < upper limit of normal [ULN]), among subjects with elevated concentrations at Baseline, at Week 12	
 Proportion of subjects with normalization of hsCRP (as defined by hsCRP < ULN), among subjects with elevated concentrations at Baseline, at Week 12

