5 SUBJECT CHARACTERISTICS

5.1 SUBJECT DISPOSITION

Tabular summaries of subject disposition will be provided for screening and IP. These summaries will include the number of subjects screened, the number of subjects screened but not enrolled (for screening period only), and the number of subjects enrolled and treated as well as the number of subjects who discontinued the respective study period, and reasons for discontinuation.

The following subject disposition summaries will be provided based on the total number of subjects screened:

- Number of subjects screened (n)
- Number of subjects screening failures (n)
- Number of subjects enrolled (n)
- Number of subjects enrolled and treated (n)

The following subject disposition summaries will be provided based on Safety Analysis Set:

- Number of subjects completed IP (n)
- Number of subjects in FAS
- Number of subjects in PP Analysis Set
- Number of subjects discontinued prematurely during IP (n)
 - Reasons for discontinuation

	STATISTICAL ANALYSIS PLAN	
---	--------------------------------------	---

Version: 02

Status: Final

The number of subjects in Safety Analysis Set will be summarized by geographic region. A listing of subject discontinuation will be provided with a reason of discontinuation indicating period (i.e., Screening or IP).

Geographic region will be defined as follows, based on the locations of sites anticipated to participate in these studies:

- North America: Canada, United States
- Western Europe: Belgium, France, ,
- Eastern Europe: Poland, Czech, Russia, Georgia, Ukraine
- Rest of World: Australia

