7.1.7 SUMMARIES OF ADVERSE EVENTS

Treatment Emergent (TE) AEs will be summarized based on the Safety Analysis Set by treatment period and post-treatment period, separately.

Summary tables will be presented to provide the number and percentage of subjects experiencing any AEs, any severe AEs, any drug-related AEs, any SAEs, any drug-related SAEs, and any AEs leading to study drug interruption or discontinuation.

In addition to the above summary table, summary tables and listings of adverse events listed below will be provided.

- Summary of TEAEs by SOC and PT
- Summary of TEAEs by SOC, PT and Max Severity
- Summary of Severe (CTCAE Grade \geq 3) TEAEs by SOC and PT
- Summary of Related TEAEs by SOC and PT
- Summary of TESAEs by SOC and PT
- Summary of Related TESAEs by SOC and PT
- Summary of AEs in Follow-up by SOC and PT
- Listing of All AEs
- Listing of TESAEs or Death
- Listing of TEAEs Leading to Study Drug Interruption or Discontinuation

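### No planned AE summary reports AEs leading to discontinuation, a named part of the primary safety endpoint, separately from AEs leading to interruption

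*SAP*

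**What the plan says.** Protocol section 3.1 defines the primary safety endpoint as "the proportion of subjects reporting AEs, SAEs, AEs leading to discontinuation, and markedly abnormal laboratory values". SAP section 2, Table 1, repeats it: "Proportion of subjects reporting AEs, SAEs, AEs leading to discontinuation, and markedly abnormal laboratory values". Neither mentions interruption.

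SAP section 7.1.7 describes an overview table giving the number and percentage of subjects in several AE categories. The last category is "any AEs leading to study drug interruption or discontinuation". The section then names seven tables by system organ class and preferred term, none of them for discontinuation, and three listings, one of which is the "Listing of TEAEs Leading to Study Drug Interruption or Discontinuation".

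Three other outputs bear on the point:
- SAP section 5.1 counts, on the Safety Analysis Set, subjects who left the induction period early, with reasons. It adds: "A listing of subject discontinuation will be provided with a reason of discontinuation".
- SAP section 5.3.2 plans a by-subject listing of drug administration and infusion interruptions.
- The protocol synopsis plans a by-subject AE listing whose fields end with "relationship to drug, and action taken, will be provided".

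Protocol section 9.2.7.1 does not fill the gap. It says "The number and percentage of subjects reporting AEs (all, serious, related) will be" tabulated, without naming AEs that led to discontinuation. SAP section 10, which lists changes from the protocol, does not mention this item.

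**The concern.** The endpoint is a proportion of subjects, and safety is the first primary objective. The other three parts of the endpoint each have a matching planned summary: AEs and SAEs in section 7.1.7, and markedly abnormal laboratory values in section 7.4, Table 8. The discontinuation part has only a row that also counts interruptions.

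The protocol treats these as different events. Section 4.6 foresees doses being withheld during clinically significant infections. Section 5.4 distinguishes an infusion that is stopped and may be restarted from permanent discontinuation. A subject who pauses and continues and a subject who stops for good carry different information about tolerability, and the joined row cannot tell them apart. In a single-arm study of this size, a few interruptions could make up most of the row.

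**Working it through.** The plan states no figure to reproduce, so the check is a comparison of texts followed by simple arithmetic.

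**Step 1. Match each part of the endpoint to a planned n (%) summary.**

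| Part of the primary safety endpoint | Planned n (%) summary | Same quantity? |
|---|---|---|
| AEs | SAP 7.1.7 overview | Yes |
| SAEs | SAP 7.1.7 overview | Yes |
| AEs leading to discontinuation | SAP 7.1.7 overview, joined with interruption | No |
| Markedly abnormal laboratory values | SAP 7.4, Table 8 | Yes |

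**Step 2. One row or two?** In the overview sentence each category opens with its own *any*. SAEs and drug-related SAEs, for example, are introduced separately. Interruption and discontinuation share a single *any*, and the listing title pairs them again as one output. The natural reading is one row. Table shells are not in the documents, so two rows cannot be excluded.

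**Step 3. Relation between the joined row and the endpoint.** Let
- N = subjects in the Safety Analysis Set;
- D = subjects with at least one AE leading to discontinuation;
- I = subjects with an AE leading to interruption and none leading to discontinuation.

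Endpoint as defined: E = D/N.
Joined row: P = (D + I)/N.
Difference: P − E = I/N.

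Since I ≥ 0, P is never below E, and the two are equal only when I = 0.

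**Step 4. Size.** N is about 50 (protocol section 8.2; SAP section 3.2). Each interruption-only subject adds 1/50 = 2 percentage points. The documents give no rate of interruption, so I is an assumption:

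| Assumed I | P − E |
|---|---|
| 0 | 0/50 = 0 points |
| 1 | 1/50 = 2 points |
| 3 | 3/50 = 6 points |
| 5 | 5/50 = 10 points |

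If D is assumed to be 2, then E = 2/50 = 4%, and P runs from 2/50 = 4% (I = 0) to 7/50 = 14% (I = 5).

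**Step 5. Do the other outputs supply E?**
- *Disposition (SAP 5.1).* The analysis set and period fit. The reason categories are not listed, so an adverse-event reason is not assured. Disposition also records why a subject left the period, not the action taken on study drug for each AE.
- *AE listing with action taken (protocol synopsis).* This would let a reader separate the two events and count subjects, but a listing gives no proportion.
- *Interruption listing (SAP 5.3.2).* This identifies interruptions but is not tied to AEs and is not a proportion.

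**The case against.** The strongest reply is that nothing is lost. Table 1 keeps the endpoint as the protocol defines it and section 10 does not redefine it. Section 7.1.7 may be only an inventory of table content, with two rows intended. Disposition with reasons uses the right analysis set and period. With about 50 subjects, the count can be read from the listings. The endpoint also does not say whether discontinuation means of study drug or of the study; if the latter, the disposition table is the more direct output. Finally, the documents give no interruption rate, and protocol section 1.4.2 reports no discontinuation or dose reduction due to AEs in the healthy-volunteer study.

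Much of this stands. A reader might infer from section 7.1.7 that the component will never be reported, or that the sponsor has redefined the endpoint. The documents support neither, because the definition is intact and other planned outputs may yield the count. A reader might also infer that the joined row must overstate the endpoint; it equals the endpoint if no subject has an interruption alone.

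The reply does not remove the mismatch. The only percentage specified in the AE section is for a broader category than the endpoint, and the alternatives are either incompletely specified or not proportions. The Phase 1 result concerns healthy volunteers and does not address interruptions. The ambiguity between study drug and study is a further reason to specify the row.

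**Conclusion.** The point holds as a conflict between a stated output and a stated primary endpoint component: no planned AE summary reports AEs leading to discontinuation as defined. The joined figure exceeds the endpoint by I/N, which is 2 percentage points per interruption-only subject at N = 50, or 0 to 10 points for an assumed 0 to 5 such subjects.

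This rests on reading section 7.1.7 as one joined row, which its wording favours but table shells could overturn, and on taking discontinuation to mean discontinuation of study drug. The range for I is illustrative only.

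The consequence is limited to reporting. SAP section 7 makes safety descriptive, with no inferential testing, so no decision rule, alpha, power or sample size depends on the row. The documents plan no cross-study safety comparison, so the point should not be argued on that ground. It is still worth correcting, because a component of a primary endpoint should not have to be reconstructed from listings.

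**What to change.** In SAP section 7.1.7, replace the joined item with two n (%) rows on the Safety Analysis Set for the induction period:
- (a) TEAEs leading to study drug discontinuation, labelled as the primary endpoint component;
- (b) TEAEs leading to study drug interruption only, meaning subjects not already counted in (a).

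The rows then add up to the present joined figure, so nothing is lost. Flag the two events separately in the existing listing. State in Table 1 that discontinuation refers to study drug or, if the sponsor means the study, say so and point to the disposition table with an explicit adverse-event reason. A table of (a) by system organ class and preferred term is optional, since the endpoint asks only for a proportion of subjects.

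The cost is one extra table row and a flag in a listing. No new data should be needed, because the protocol synopsis already plans to list action taken for each AE. If the SAP is not reopened, its section 1 allows the change to be documented with its rationale in the clinical study report.

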7.2 PHYSICAL EXAMINATION

Physical examination is performed at the screening visit. All abnormal findings will be presented in a by-subject listing.

7.3 VITAL SIGNS

Descriptive statistics will be provided by treatment group for vital signs (blood pressure (mm Hg), heart rate (bpm), respiratory rate, temperature, weight (kg), height (m) and BMI (kg/m²)) as follows:

- Baseline values
- Values at each post-baseline visit
- Change from baseline at each post-baseline visit

Body mass index (BMI) will be calculated from height and weight measurements collected at screening and Week 12/EOT using the following formula:

$$\text{BMI} = \text{Weight (kg)} / [\text{Height (m)}]^2.$$

A by-subject listing of vital signs will be provided by treatment group, subject ID number and visit in chronological order.

Subjects with markedly abnormal vital signs (criteria depicted in Table 7) will be summarized by study period.

Table 7 Markedly Abnormal Vital Signs

Markedly Abnormal Vital Signs	
Weight	increase or decrease \geq 20% from Baseline
Heart Rate	(Increase of $>$ 20 bpm from Baseline and $>$ 120 bpm) OR (decrease of $>$ 20 bpm and $<$ 60 bpm)
SBP	(Increase of $>$ 20 mmHg from Baseline AND $>$ 160 mmHg) OR (decrease of $>$ 20 mmHg from Baseline AND $<$ 80 mmHg)

DBP	(Increase of >20 mmHg from Baseline AND >100 mmHg) OR (decrease of >20 mmHg from Baseline AND <60 mmHg)
-----	--

7.4 CLINICAL LABORATORY TESTS

Descriptive statistics will be provided by treatment group for each laboratory test (hematology, serum chemistry, and urinalysis) specified in the study protocol as follows:

- Baseline values
- Values at each post-baseline visit
- Change from baseline at each post-baseline visit

Tabulated tables will be presented by showing change in lab normal range (low, normal, and high) for clinical laboratory values by treatment group. A shift table describing out-of-normal range shifts will be provided for clinical laboratory results.

In the by subject listings, laboratory values which fall outside the reference ranges and abnormal findings will be flagged. The listing will include treatment group, subject ID, laboratory collection date/time, analyte name, and analyte finding.

Subjects with markedly abnormal lab values (criteria depicted in Table 8) will be summarized by study period.

Table 8 Markedly Abnormal Laboratory

Markedly Abnormal Laboratory	
Hematology	
Hemoglobin	<8.0 g/dL
Platelet	<50,000/mm ³
WBC	<2000/mm ³
Neutrophils (absolute)	<1000/mm ³
Lymphocytes (Absolute)	<500/mm ³ or >200,00/mm ³
Chemistry	
ALT	>5 X ULN
AST	>5X ULN
Alkaline phosphatase	>5 X ULN
Total bilirubin	>3X ULN
GGT	>5X ULN
Potassium	>6.0 mmol/L or <3.0 mmol/L
Sodium	>155 mmol/L or <130 mmol/L
Cholesterol	>400 mg/dL
CPK	>5X ULN
Creatinine	>3X ULN or 3X of Baseline

Calcium	>12.6 mg/dL or <7 mg/dL
Glucose	>250 mg/dL or <40 mg/dL
Triglyceride	>500 mg/dL
Albumin	<2 g/dL

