#### 4.5 Removal of Subjects from Study

A genuine effort must be made to determine the reason(s) why a subject fails to return for the necessary visits or is discontinued from the study. This information and date must be recorded on the appropriate eCRF and on the Termination Sheet. Subjects MUST discontinue from the study for any of the following reasons:

- The subject decides that it is in his/her best interest. It is fully understood that all subjects volunteer for the study and that they may withdraw their consent to continue in the study at any time.
- Any AE, laboratory abnormality, or change in medical condition which, in the opinion of the Investigator, indicates that continued participation in the study is not in the best interest of the subject.
  - For potential drug induced liver injury (DILI), timely confirmation of initial liver-related laboratory abnormalities should be performed. Potential drug induced liver injury is defined as:
    - ALT/AST elevation  $>3$  x ULN, AND
    - Total bilirubin  $>2$  x ULN, without initial findings of cholestasis (elevated serum alkaline phosphatase), AND
    - No other immediately apparent possible cause of increased ALT/AST and total bilirubin, such as viral hepatitis A, B, or C; preexisting or acute liver disease; or other drug capable of causing the observed injury
  - Subjects with suspected DILI should be discontinued from the study
- Persistent non-compliance of the subject
- Pregnancy

- Use of any investigational drug therapy for CD excluding study treatment
- Treatment with biologic therapy for CD

The Investigator must notify the Medical Monitor by telephone or by email as soon as possible if any subject prematurely withdraws from the study. The date when the subject is withdrawn and the reason for discontinuation must be recorded in the eCRF. If a subject is “lost to follow-up” (fails to return for study visits), a reasonable effort should be made to contact the subject in order to determine why the subject failed to return. This information must be documented in the eCRF. If a subject is withdrawn from the study early (regardless of the cause) all of the end-of-study evaluations should be performed at the time of withdrawal, and the subject followed for 12 weeks after the last dose of PRA023, if possible, due to the long  $t_{1/2}$  of PRA023.

It is agreed that, for reasonable cause, either the Investigator or the Sponsor, Prometheus, may terminate this study.

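### SAP Table 8 has no combined transaminase–bilirubin criterion, so a subject can meet the laboratory part of the protocol's potential-DILI definition without being counted by any ALT, AST or bilirubin row

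*SAP*

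**What the plan says.** Protocol section 3.1 makes laboratory findings part of the primary safety endpoint: "AEs leading to discontinuation, and markedly abnormal laboratory values". The SAP repeats this in its table of objectives and endpoints: "Proportion of subjects reporting AEs, SAEs, AEs leading to discontinuation, and markedly abnormal laboratory values". The protocol does not say what makes a value markedly abnormal. SAP section 7.4 supplies the only criteria: "Subjects with markedly abnormal lab values (criteria depicted in Table 8) will be summarized by study period". The liver rows of Table 8 are ALT, AST, alkaline phosphatase and GGT, each above 5x ULN, and "Total bilirubin >3X ULN". Each row stands alone.

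Protocol section 4.5 has a liver rule of a different kind. It opens with "For potential drug induced liver injury (DILI), timely confirmation of initial liver-related laboratory abnormalities should be performed" and then joins three conditions. The first is ALT/AST above 3x ULN. The second is "Total bilirubin $>2$ x ULN, without initial findings of cholestasis (elevated serum alkaline phosphatase), AND". The third is that no other cause is immediately apparent. The stated consequence is "Subjects with suspected DILI should be discontinued from the study".

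The SAP never mentions DILI. Its events of special interest (section 7.1.5) are infusion reactions, peri-infusion reactions and infections.

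**The concern.** The protocol singles out one laboratory pattern in the liver as a reason to stop a subject's participation, and defines it by two moderate elevations occurring together. The SAP's laboratory component looks only for one large elevation at a time. The two rules therefore do not nest: some subjects meet the laboratory part of the first and none of the ALT, AST or bilirubin rows of the second.

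At stake is how far the laboratory component of a primary endpoint can be trusted. A reader who sees no subjects in the ALT, AST and bilirubin rows could take it that the protocol's liver pattern did not occur. The table cannot support that reading.

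**Working it through.** The plan states no figure to reproduce on this point, so the check is a comparison of two threshold rules.

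Inputs, in multiples of ULN:

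- Protocol 4.5, laboratory part: (ALT > 3 or AST > 3) and total bilirubin > 2.
- SAP Table 8, transaminase and bilirubin rows: ALT > 5, or AST > 5, or total bilirubin > 3.

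The missed region is where the first rule is true and the second false. That requires peak ALT and peak AST both at or below 5x with at least one above 3x, and peak bilirubin above 2x but not above 3x.

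| ALT or AST (x ULN) | Bilirubin (x ULN) | Protocol 4.5 laboratory part | Table 8 ALT, AST or bilirubin row |
|---|---|---|---|
| 3.1 | 2.1 | met | none |
| 4.0 | 2.5 | met | none |
| 5.0 | 3.0 | met | none |
| 5.1 | 2.1 | met | ALT/AST row |
| 3.1 | 3.1 | met | bilirubin row |
| 6.0 | 1.0 | not met | ALT/AST row |

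On a grid in steps of 0.1x ULN, the missed region runs from 3.1 to 5.0 for the transaminase and from 2.1 to 3.0 for bilirubin: 20 × 10 = 200 grid points. Adding a row with the protocol's laboratory thresholds flags all 200 and leaves none missed.

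Could another part of the SAP pick up the pattern?

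- Other Table 8 rows: alkaline phosphatase above 5x cannot be relied on, because the protocol's definition excludes initial cholestasis. GGT above 5x, or a non-liver row, would flag the subject only by coincidence.
- Shift tables (SAP 7.4): they use low, normal and high, so 1.1x and 4.9x ULN fall in the same cell, and analytes are not combined.
- Listings (SAP 7.4): out-of-range values are flagged analyte by analyte, so a reader would have to assemble the pattern by hand.
- Adverse event tables (SAP 7.1.7): these are organised by system organ class and preferred term, with no laboratory combination.

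Scale, for illustration: one such case among 50 subjects is 1/50 = 2.0%. The Wilson 95% interval has centre (0.02 + 3.84/100)/(1 + 3.84/50) = 0.054 and half-width 1.96 × √(0.02 × 0.98/50 + 3.84/10,000)/(1 + 3.84/50) = 0.051, which gives 0.4% to 10.5%. The SAP plans no inferential testing of safety, so this shows scale only.

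**The case against.** The strongest reply is that the subject is not lost. Protocol section 7.2 treats a laboratory abnormality that leads to stopping study drug as clinically significant, to be reported as an adverse event. SAP section 7.1.7 then tabulates and lists events leading to interruption or discontinuation. Such a subject would enter the primary safety endpoint through the adverse event components, and the individual values would be flagged in the listings. This stands. A reader might infer that a liver-injury discontinuation could vanish from the primary safety endpoint or be tabulated nowhere; the documents do not support that.

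A second reply is that the two rules serve different purposes. Section 4.5 manages individual subjects and requires confirmation, absence of initial cholestasis and no other apparent cause. Table 8 is a descriptive display, and nothing says it must reproduce discontinuation criteria. This stands in part. ALT 4x with bilirubin 2.5x does not by itself make a subject one who has to be discontinued, and it would be wrong to read it so. But Table 8 is also the sole definition of a primary endpoint component, and leaving out the one liver pattern the protocol names is a gap in that component.

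Third, the gap is bounded. Once either analyte passes its Table 8 limit, the subject is counted, although only as a single-analyte elevation. ALT 6x with bilirubin 2.5x is already in the count. Safety is descriptive, so no test result changes. All of this is correct and limits the weight of the point.

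What remains is that the adverse event route depends on the investigator recognising the combination and acting on it. A programmed count from the laboratory data would be an independent check, and the SAP has none.

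**Conclusion.** The point holds in a limited form. The laboratory component of the primary safety endpoint does not count, through any ALT, AST or bilirubin row, a subject with ALT/AST above 3x and up to 5x ULN and total bilirubin above 2x and up to 3x ULN, although that subject meets the laboratory part of the protocol's potential-DILI definition. No SAP output identifies the combination. The gap lies in one component and one window of values; it is not a failure of the whole endpoint.

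The size in this trial is unknown because the documents give no event rate; the 2% figure assumes exactly one case among 50. The conclusion rests on reading Table 8's rows as independent and on no other row being crossed. The protocol does not say whether the two elevations must be concurrent, so any programmed count identifies candidates and not confirmed cases. Which thresholds are clinically right is not judged here.

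**What to change.** Reconcile protocol section 4.5 and SAP section 7.4 as follows:

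- Add to the Table 8 summary a separately labelled row for candidate potential DILI, using the protocol's own laboratory thresholds: ALT or AST above 3x ULN with total bilirubin above 2x ULN. Keep all existing rows.
- State in the SAP how concurrency is determined, since the protocol does not say.
- List each subject in the row with the alkaline phosphatase values and the investigator's assessment of cause, so that cholestatic or otherwise explained cases can be told apart.

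The cost is one table row and one listing. ALT, AST, bilirubin and alkaline phosphatase are all in the chemistry panel already scheduled at Weeks 0, 2, 6 and 12 and at early termination (protocol Table 2), so no new data are needed. A compound criterion also fits the SAP's format: Table 7 already combines conditions for heart rate and blood pressure. The downside is that the reported proportion may be slightly less favourable and may include cases later attributed to another cause; the separate label and the listing deal with that. No threshold or clinical rule changes. The SAP already provides for changes after finalisation to be documented, with the rationale, in the clinical study report.
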